3.2.1 Planned number of participants

20 participants in good general health aged 18 or over, will be accepted onto the study in order to obtain sufficient examples of gingival health/disease across the range of gingival mucosa pigmentation for each of the 4 groups listed below, 5 participants will be recruited on the basis of their predominant DOPI obtained from simple visual examination, for whom both inflamed and non-inflamed gingivae are visible.

GROUP 0

DOPI Score 0 - No clinical pigmentation (pink-coloured gingiva)

5 participants with predominant DOPI 0

GROUP 1

DOPI Score 1 - mild clinical pigmentation (mild light brown pigmentation)

5 participants with predominant DOPI 1

GROUP 2

DOPI Score 2 - moderate clinical pigmentation (medium brown or mixed pink and brown pigmentation)

5 participants with predominant DOPI 2

GROUP 3

DOPI Score 3 - heavy clinical pigmentation (deep brown or blue-black pigmentation)

5 participants with predominant DOPI 3

Intra-oral photographic examples of the different DOPI scores, BOP and gingival inflammation features will be taken.

The selection of suitable participants will be made according to the inclusion and exclusion criteria described in the following sections.

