5.1 Sample Size Calculation

With 5 participants recruited to each of 4 groups defined by predominant DOPI, there are potentially up to $24 \times 6 \times 20 = 2880$ sites available for study. We assume conservatively that at least 800 bleeding and 800 non-bleeding sites will be scored across the 4 DOPI groups.

For the primary objective, we set a 75% target for sensitivity and specificity for on-scan dichotomised MGI to identify clinical binary BI, corresponding to that used in the recession and plaque studies, and calculate the resulting projected confidence interval width. An ordinary (Wald) 95% confidence interval for an observed proportion of 75% based on a sample of size 800 is from 72.0% to 78.0%. However, this needs to be widened to take account of non-independence within subjects. In these precedent studies, the resulting bootstrap intervals were widened by a factor around 2.5. So the anticipated confidence interval width for either parameter is from 67.5% to 82.5%.

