5.3 Statistical Methods

For the binary variables studied – on-scan dichotomised MGI to identify clinical binary BI, and gingival phenotype on-scan vs clinical, sensitivity and specificity will be reported, with bootstrap confidence intervals to take account of non-independence within subjects.

These analyses will be run based on all 4 pigmentation groups together. Separate sensitivity and specificity estimates will also be calculated for low and high pigmentation groups and contrasted.

On scan and clinical pigmentation scores will be compared by crosstabulation and calculating misclassification probabilities.

Corresponding analyses at participant level will be developed using either an average score across sites, or for pigmentation, a maximum score.

6. Monitoring

Monitoring of studies is conducted in by the sponsor according to Good Clinical Practice (GCP) (ICH. Topic e6 (r2) guideline for good clinical practice. Nov 2016). The monitor must maintain the confidentiality of the study documents.

7. Data Handling and Record Keeping

There will be at least one CRF for each participant entered into the study. It is the responsibility of the PI to ensure the completeness and accuracy of the CRF and to authorise only trained members of staff to complete the CRF.

The CRF must be completed legibly, using a black ballpoint pen. Erroneous values and/or text must not be obliterated. Instead, the error must be crossed out with a single line, the correct value/text added, and the correction signed or initialled and dated.

There will be study specific records to record the identification of any data to be recorded directly on the CRFs or other written or electronic record of data, and to be considered to be source data.

All site staff must ensure that the participant's anonymity will be maintained. On all documents participants must be identified only by an identification code and not by their names. The PI or designee must keep a separate confidential enrolment log that matches identifying codes with the participant's names. The PI or designee must maintain these documents at the site.

It is the responsibility of the PI or designee to maintain adequate clinical study records. Copies of all study material must be archived for a period of at least 15 years after the end of the study (or more as legally required). All documents must be archived in a secure place and treated as confidential material.

8. Quality Standards

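### Bootstrap intervals on 20 participants need a small-sample form: the usual ones would cover about 91–93% pooled and 87–90% in a pigmentation group of 10

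*Protocol*

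**What the plan says.** Protocol section 5.3 gives sensitivity and specificity for the binary variables (on-scan inflammation against bleeding, and phenotype) "with bootstrap confidence intervals to take account of non-independence within subjects". The analysis is run on all four groups together. Then "Separate sensitivity and specificity estimates will also be calculated for low and high pigmentation groups and contrasted". Low and high are not defined, and neither the type of bootstrap nor any small-sample correction is stated.

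Section 5.1 fixes the numbers: "With 5 participants recruited to each of 4 groups defined by predominant DOPI", hence 20 participants, and "We assume conservatively that at least 800 bleeding and 800 non-bleeding sites will be scored across the 4 DOPI groups". Its precision argument starts from a binomial interval ("An ordinary (Wald) 95% confidence interval for an observed proportion of 75% based on a sample of size 800 is from 72.0% to 78.0"%) and widens it for clustering: "In these precedent studies, the resulting bootstrap intervals were widened by a factor around 2.5". The projected interval is 67.5% to 82.5%.

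**The concern.** A bootstrap that allows for dependence within subjects has to resample participants. The effective sample is then 20 units pooled and, if low means DOPI 0–1 and high means DOPI 2–3, 10 units in each pigmentation group. With k units the usual bootstrap estimates the variance with divisor k instead of k − 1 and refers it to something close to a normal distribution. Both make the interval too narrow, and more so as k falls.

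This matters because the sample size is justified by interval width alone. The primary objective (section 2.1) concerns accuracy across the range of pigmentation, so the low and high estimates and their contrast are central, and the separate low and high estimates are where the shortfall is largest.

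**Working it through.** **Inputs from Protocol section 5.1:** target 75%; 800 sites per parameter; 20 participants; widening factor about 2.5.

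**Assumptions:** 10 participants each in low and high; the same true sensitivity in every group; beta-binomial sites; coefficient of variation (CV) of sites per participant of 0 to 0.8.

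**1. The protocol's own figure.** 1.96 × √(0.75 × 0.25 / 800) = 3.0 points, giving 72.0% to 78.0%. Multiplied by 2.5 this is 7.5 points, giving 67.5% to 82.5%. It reproduces.

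**2. Implied clustering.** Design effect 2.5² = 6.25. Mean cluster size 800 / 20 = 40. ICC = (6.25 − 1) / (40 − 1) = 0.135.

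**3. Normal-theory approximation.** Coverage = 2·T(k−1)[1.96 × √((k−1)/k)] − 1, with T(k−1) the t distribution function on k − 1 degrees of freedom.
- k = 20: 1.96 × √0.95 = 1.910, coverage 92.9%. Width factor needed for 95%: 2.093 / 1.910 = 1.10.
- k = 10: 1.96 × √0.90 = 1.859, coverage 90.4%. Width factor needed: 2.262 / 1.859 = 1.22.

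**4. Simulated coverage (%), resampling whole participants,** 75% true value, ICC 0.135, 999 resamples, 4,000 runs (normal interval 3,000 runs). Monte Carlo error is about half a point.

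| Interval | k = 20: CV 0 / 0.5 / 0.8 | k = 10: CV 0 / 0.5 / 0.8 |
|---|---|---|
| Percentile | 92.2 / 91.2 / 90.7 | 90.4 / 88.8 / 87.3 |
| Normal | 93.3 / 91.3 / 90.1 | 89.9 / 87.2 / 85.4 |
| BCa | 93.0 / 91.2 / 89.9 | 90.9 / 89.3 / 86.4 |
| Studentised (bootstrap-t) | 95.4 / 94.8 / 94.0 | 95.8 / 94.5 / 93.3 |

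For the 10 v 10 difference the percentile interval covers 91.5%, 90.4% and 90.5% at CV 0, 0.3 and 0.6. Over ICC 0.05 to 0.25 at 75%, percentile coverage is about 90–93% with 20 and 87–91% with 10.

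**5. The jackknife.** A delete-one-participant jackknife on the logit scale with t on k − 1 degrees of freedom covers 94.7–96.0% with 20 and 93.3–95.6% with 10 (CV 0 to 0.6). At CV 0.8 a further 3,000 runs gave 94.3% and 93.0%. With 10 participants its mean half-width is 12.0–13.4 points, against 9.7–10.3 for the percentile interval.

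**6. Resampling within DOPI group.** Without a correction, stratifying makes matters worse, because each stratum has only 5 participants: percentile coverage pooled is about 89%. With studentising that uses the within-stratum k − 1 divisor, 3,000 runs at CV 0, 0.5 and 0.8 gave 96.0%, 95.0% and 94.8% pooled, and 96.3%, 94.1% and 93.5% with 10.

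**7. Width relative to the unstratified percentile interval (same runs).** Jackknife: 1.11–1.17 pooled and 1.24–1.32 with 10. Stratified bootstrap-t: 1.20–1.39 pooled and 1.49–1.86 with 10.

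**The case against.** The strongest reply is that the protocol does not commit to a faulty interval. Section 5.3 names no bootstrap type, and a studentised bootstrap over participants fits its wording and nearly holds 95%. Interval type and number of resamples are ordinary SAP content, and the SAP is not at hand. This stands: the text is not wrong, and the point is conditional on a usual form being used. What remains is that three of the common forms fall short at these numbers, BCa included, and nothing in the protocol points to the one that does not.

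The pooled effect is also modest. A half-width of 7.5 points times 1.10 is 8.25, so 67.5–82.5% becomes about 66.8–83.3%. For a pilot described in section 3.1 as observational, that changes little. This also stands; the case is stronger for the low and high groups.

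The figures rest on assumptions. The ICC is back-calculated from an approximate factor taken from studies whose participant numbers are not given, and the 10/10 split is a reading of undefined terms. Hence ranges are given.

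A reader might infer two stronger points. One is that intervals within a single DOPI group ("5 participants with predominant DOPI 0") would be worse still; but section 5.3 plans no such intervals. The other is that false pigmentation differences would be declared too often; but the protocol says only that the estimates are contrasted. It states no test and no rule for declaring a difference or for comparing an interval with the 75% target.

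**Conclusion.** The point holds as a conditional one. If section 5.3 is carried out with a percentile, normal or BCa bootstrap over participants, nominal 95% intervals cover about 91–93% pooled, about 87–90% in a pigmentation group of 10, and about 90–92% for the difference. The lower ends belong to very uneven numbers of bleeding sites per person, where the normal and BCa forms can fall a point or two further. The size depends on the assumed ICC, cluster-size variation, beta-binomial form and 10/10 split; the direction does not change over the ranges tried. It is a cheap improvement to the analysis, not an error in what the protocol states.

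**What to change.** In section 5.3 (or in the SAP, with a reference from 5.3), specify one interval for the pooled estimates, the low and high estimates and their contrast, and define low and high. Either of these would do:

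- **Delete-one-participant jackknife** on the logit scale, with t degrees of freedom from the number of participants (19 pooled, 9 in a group of 10). For the contrast, combine the two groups' jackknife variances and use 18 degrees of freedom.
- **Studentised bootstrap** resampling whole participants within DOPI group, with a standard error that uses the within-group k − 1 divisor. Stratified resampling should not be adopted without the studentising.

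The change is to analysis wording only and needs no further participants. The price is width: for the jackknife roughly 10–17% pooled and 20–35% per pigmentation group; the stratified bootstrap-t was wider in simulation (20–39% and 49–86%). On cost the jackknife is preferable; its coverage with 10 participants and very uneven site counts is still slightly below 95%, at about 93%. If accuracy differs between DOPI groups, an unstratified jackknife errs on the wide side for the pooled estimate.

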Appendix A – Oral pigmentation index (DOPI) (Dummett et al 1964)

This index of oral pigmentation is commonly used due to its simplicity and ease of use. The scores are as follows:

- Score 0 - No clinical pigmentation (pink-coloured gingiva)
- Score 1 - Mild clinical pigmentation (mild light brown colour)
- Score 2 - Moderate clinical pigmentation (medium brown or mixed pink and brown colour)
- Score 3 - Heavy clinical pigmentation (deep brown or bluish black colour)

The gingivae will be scored at 6 points around the tooth, (mesiobuccal, buccal, distobuccal, mesiolingual, lingual, distolingual) using the oral pigmentation index.

Appendix B – Bleeding on probing index (BI) (Ainamo & Bay,1975).

Method of examination:

A UNC15 periodontal probe is passed into the gingival crevice at six separated points (mesiobuccal, buccal, distobuccal, mesiolingual, lingual, distolingual) and if bleeding occurs within 10 to 15 seconds, a positive score of 1, is given. It has been shown that the scores obtained with this index correlate substantially with GI (Löe and Silness, 1963) and MGI (Lobene et al 1986) this has been used in profile studies and short-term studies.

Scoring criteria:

- 0 Absence of bleeding
- 1 Presence of bleeding

Appendix C – Visual gingival inflammation features

The Modified Gingival Index (MGI) (Lobene et al, 1986) was developed as a non-invasive (no probing technique) to the assessment of gingival inflammation, not requiring probing, thus suitable for use on-scan.

The following criteria are adopted:

Score	Criteria
0	Absence of inflammation
1	Mild inflammation or with slight changes in color and texture but not in all portions of gingival marginal or papillary
2	Mild inflammation, such as the preceding criteria, in all portions of gingival marginal or papillary
3	Moderate, bright surface inflammation, erythema, edema and/or hypertrophy of gingival marginal or papillary
4	Severe inflammation: erythema, edema and/or marginal gingival hypertrophy of the unit or spontaneous bleeding, papillary, congestion or ulceration

Gingival margins on the intra-oral images will be scored at 6 sites, (mesiobuccal, buccal, distobuccal, mesiolingual, lingual, distolingual) as 0 (health/minimal gingivitis score 0-1 on the MGI index) or 1 (gingivitis score 2-4 on the MGI index). The examiner will also record descriptors such as change in morphology or colour.

Appendix D – 3D Intra-oral Assessment

A 3D intra-oral scan of the participant’s mouth will be obtained using a 3Shape Trios intra-oral scanner and stored using the participant’s unique identification number.

At least 2 weeks after the clinical examination, the study examiner will perform the gingival assessments visually from the IOS 3D models for 7-7 teeth, scoring visual gingival inflammation features - as described in Appendix C, Dummett-Gupta Oral Pigmentation Index (DOPI) score (Appendix A), and thick or thin gingival phenotype assessment (Appendix E), blinded to the preceding clinical assessments.

Appendix E – Gingival phenotype clinical assessment (Jepson et al 2018).

Gingival phenotype will be assessed by using a UNC15 periodontal probe to measure the gingival thickness (GT) observing the periodontal probe shining through gingival tissue after being inserted into the sulcus:

- 0)** Probe visible: thin (≤ 1 mm).
- 1)** Probe not visible: thick (> 1 mm).

One buccal and one lingual score will be recorded for each tooth.

Note: Probe visibility was tested in samples of subjects with specified gingival pigmentation. It is unknown whether the same outcomes are to be expected in populations with different gingival pigmentations.

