2.2 Secondary Objectives

- To assess the diagnostic accuracy and agreement between gingival pigmentation assessments derived from clinical examination and intraoral scans using the Dummett Oral Pigmentation Index (DOPI)
- To compare the diagnostic accuracy and agreement of the on-scan assessment in detecting gingival inflammation, defined as BOP-positive sites clinically, stratified by gingival phenotype, i.e., thin and thick.

3. Study Design

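### The thin/thick phenotype strata rest on probe visibility, whose transfer across pigmentation the protocol calls unknown, so they may be confounded with DOPI

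*Protocol*

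**What the plan says.** Appendix E of the protocol reads phenotype by "observing the periodontal probe shining through gingival tissue after being inserted into the sulcus". A visible probe is scored as thin (1 mm or less) and an invisible one as thick (more than 1 mm). A note there adds: "Probe visibility was tested in samples of subjects with specified gingival pigmentation". It then says: "It is unknown whether the same outcomes are to be expected in populations with different gingival pigmentations". It does not say which pigmentation levels were tested.

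Section 3.2.1 fills four groups of five by predominant DOPI (0, 1, 2 and 3), the last being "5 participants with predominant DOPI 3".

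Phenotype is used twice. The second objective in section 2.2 assesses on-scan detection of inflammation, "defined as BOP-positive sites clinically, stratified by gingival phenotype, i.e., thin and thick". Section 5.3 also lists "gingival phenotype on-scan vs clinical, sensitivity and specificity will be reported, with bootstrap confidence intervals", which makes the clinical reading the reference standard. The same section runs its analyses on all four groups together and adds separate estimates for low and high pigmentation. It does not state thin and thick accuracy against bleeding within a pigmentation level.

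Section 3.4.2 calibrates the examiner on phenotype against a gold standard examiner in 10 volunteers. No independent measure of thickness is named.

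**The concern.** A probe can fail to show because the tissue is thick or because it is dark. If darkness contributes, sites labelled thick will include too many pigmented sites. Pigmentation is also the factor whose effect on scan accuracy is the primary question. A difference between the thin and thick strata could then be pigmentation under another name, and a reader could take it for an effect of tissue thickness.

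The on-scan phenotype comparison has a related weakness. If thin sites are read as thick more often in dark tissue, the reference is wrong to a degree that depends on DOPI. Its sensitivity and specificity would then not describe accuracy for true thickness. The direction of that distortion depends on whether the on-scan reading shares the error.

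Appendix E discloses the limitation, but no step in the design or the stated analysis follows from it.

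**Working it through.** **The protocol's own precision figure.** Section 5.1 gives 75% with n = 800: 1.96 × √(0.75 × 0.25 / 800) = 0.030, so 72.0% to 78.0%. Widened by 2.5, the half-width is 7.5 points, so 67.5% to 82.5%. Both intervals reproduce. No precision figure is given for phenotype.

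**Inputs for the illustration.** From the protocol: four equal DOPI groups. Assumed, because the protocol gives no values:
- true thin share t of 30%, 50% or 70%, the same at every DOPI level;
- probability m that a thin site is read as thick, rising with DOPI as shown in the table; thick sites are always read as thick;
- on-scan sensitivity of 80% at DOPI 0–1 and 70% at DOPI 2–3, or 85% and 65%; both pairs average the 75% target;
- no true effect of phenotype on sensitivity;
- bleeding unrelated to DOPI or phenotype, so the same weights apply to bleeding sites.

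**Formulas.** In DOPI group d the share read as thin is t(1 − m_d) and the share read as thick is 1 − t(1 − m_d). The DOPI 2–3 share of each stratum is the sum over d = 2, 3 divided by the sum over all four groups. The spurious thin-minus-thick difference is (sensitivity at low DOPI − sensitivity at high DOPI) × (DOPI 2–3 share in thick − DOPI 2–3 share in thin).

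**One case in full** (t = 50%, m = 0/20/50/80%, sensitivity 85/65%):
- thin: (0.5 + 0.2) / (1 + 0.8 + 0.5 + 0.2) = 0.7 / 2.5 = 28.0%;
- thick: (0.75 + 0.90) / (0.50 + 0.60 + 0.75 + 0.90) = 1.65 / 2.75 = 60.0%;
- difference: 0.20 × (0.600 − 0.280) = 6.4 points.

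**All cases** (three values are for t = 30 / 50 / 70%):

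| m at DOPI 0/1/2/3 | DOPI 2–3 in thin | DOPI 2–3 in thick | Difference, 80/70% | Difference, 85/65% |
|---|---|---|---|---|
| none | 50.0% | 50.0% | 0 | 0 |
| 0/10/20/30% | 44.1% | 52.0 / 54.3 / 58.6% | 0.8 / 1.0 / 1.5 | 1.6 / 2.0 / 2.9 |
| 0/10/30/60% | 36.7% | 53.9 / 58.0 / 64.7% | 1.7 / 2.1 / 2.8 | 3.4 / 4.3 / 5.6 |
| 0/20/50/80% | 28.0% | 55.1 / 60.0 / 67.1% | 2.7 / 3.2 / 3.9 | 5.4 / 6.4 / 7.8 |

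If sensitivity does not vary with DOPI, the first factor is zero and so is the difference, however strong the misreading.

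**A second set of assumptions.** Take half of sites thin, sensitivity 80% at low and 60% at high pigmentation, and the probe visible at 90% of thin low-DOPI sites and at 5% of thick sites. If it is visible at 50% of thin high-DOPI sites, P(read thin) is 0.475 at low and 0.275 at high DOPI. The high-DOPI shares are 0.275 / 0.750 = 36.7% of thin and 0.725 / 1.250 = 58.0% of thick, a difference of 4.3 points. At 30% visible the shares are 26.9% and 61.1%, a difference of 6.8 points.

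**On-scan phenotype against clinical.** At one DOPI level, the share of sites the reference calls thick that are truly thin is tm / (tm + 1 − t). With t = 0.5 this is 0 for m = 0, 0.15 / 0.65 = 23% for m = 0.3 and 0.40 / 0.90 = 44% for m = 0.8. A scan that read true thickness without error would then agree with the thick reference at 100%, 77% and 56% of those sites. Here error in the reference is enough; no second condition is needed.

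**The case against.** The strongest reply is that the protocol says only that transfer is unknown. A reader might infer that the strata are confounded and the comparison biased, or that visibility fails at DOPI 2–3. The documents support neither. They do not say which pigmentation was tested, that visibility fails in dark tissue, or in which direction it would err. Bias in the bleeding analysis needs both DOPI-dependent misreading and DOPI-dependent scan accuracy, and neither is established. This stands, and it limits the point to what may happen.

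A reader might also infer that an unadjusted thin-versus-thick test is planned. It is not stated. The objective can be read as stratum-specific accuracy, which is a valid description of probe-visible and probe-not-visible sites. What remains is the label: Appendix E calls those strata thin and thick and attaches a millimetre cut.

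The low/high pigmentation split in section 5.3 can be read as covering on-scan phenotype against clinical. That is a fair partial answer for that comparison. It does not give thin and thick accuracy against bleeding within pigmentation level.

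The illustrated differences lie near or within sampling error: at most 7.8 points, against a half-width of 7.5 on all 800 sites and wider in any stratum. That is true, but the error would be systematic, so more sites would not remove it.

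Finally, cross-classification could be left to the SAP, which was not available here. The method, the label and stratification by phenotype alone are, however, fixed in the protocol.

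**Conclusion.** The point holds in conditional form. The protocol applies a phenotype reading across DOPI 0–3 while stating that its validity across pigmentation is unknown, and it stratifies a secondary objective on that reading without stating any account of DOPI. The thin/thick strata may therefore carry pigmentation. The illustrated size is about 1 to 8 points of sensitivity, resting wholly on the assumed thin share, misreading and sensitivity gradient. The reference for on-scan phenotype may also be in error to a degree that depends on DOPI. The low cost of the remedy, more than any demonstrated bias, is the reason to act.

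**What to change.** 1. Tabulate the share of probe-visible sites by clinical DOPI.
2. Report on-scan accuracy against bleeding for the two phenotype strata within low and high pigmentation, or adjusted for DOPI, with the bootstrap resampling participants. State how the 2 phenotype scores per tooth map to the 6 bleeding and DOPI sites (section 3.1).
3. Confirm that on-scan phenotype against clinical is also reported by low and high pigmentation.
4. Describe the strata as probe visible and probe not visible, and do not attribute differences to tissue thickness where visibility varies with DOPI.

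All the data are already collected; the cost is wording, a mapping rule and loss of precision. If the 800 bleeding sites split evenly and the 2.5 factor still applied (both assumptions), the half-width would be 7.5 × √2 = 10.6 points in each of two strata and 7.5 × 2 = 15.0 points in each of four cells. The cross-classified results should be labelled exploratory. A phenotype-by-DOPI interaction model would be poorly supported with 20 participants. Adjustment removes mixing across DOPI but does not recover true thickness, because no independent measure of it is planned.
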